1 INTRODUCTION

Atrial fibrillation (AF) is the most common cardiac arrhythmia and is associated with increased mortality, morbidity and impaired quality of life. Catheter ablation has become the standard of care for symptomatic patients with drug-refractory AF and the cornerstone of ablation is the electrical isolation of the pulmonary veins (pulmonary vein isolation = PVI).¹ Long-term effectiveness of an approach based on PVI as the sole ablation strategy is reported to be high for patients with paroxysmal AF (81.6% at 12 months, 73.8% at 24 months, and 68.1% at 36 months).² However, the success rate of PVI is significantly lower with only up to 51% in patients with persistent AF.³ It is assumed that this is due to the fact that persistent AF is often driven by focal and reentrant activity in the atrial substrate rather than in the pulmonary veins.⁴ Accurate, enhanced mapping techniques that can localize those extra PV sources are essential to identify and guide ablation of these sources independently from PVI.

Narayan, et al., used a 64 pole-basket catheter to map AF using unipolar electrograms recorded in the right and the left atrium to construct spatiotemporal source maps.⁵ The technology was called Focal Impulse and Rotor Modulation (FIRM). Compared with patients undergoing conventional AF ablation, FIRM guided ablation initially seemed to be associated with a higher acute success and a better outcome as demonstrated in non-randomized studies. However, in randomized multi-center studies, significant benefit of FIRM guided ablation was not confirmed.⁶

Since Narayan's pioneer work several other systems were developed to invasively map rotational activities: Biosense Webster Carto Finder uses phase mapping applied to 64-pole basket catheter unipolar electrograms to identify rotors in the atrial wall.⁷ Acutus medical uses dipole density mapping with a 48-pole non-contact basket catheter to identify sources of excitation; CardioNXT uses small spiral catheters to search for AF-sources based on typical source pattern cross-correlation with coronary sinus catheter signals; Volta Medical detects dispersion of activation maps in bipolar electrogram signals recorded using the PentaRay catheter with five splines and 20 poles.^{8,9,10} However, none of these newer mapping systems have demonstrated the clinical relevance of these extra-pulmonary vein sources of excitation in the atrial myocardium over a period longer than a few seconds. As such, the ability to identify and ablate relevant non-pulmonary vein foci/triggers to improve freedom from AF post-ablation has not been achieved to date.

The recently developed Electrographic Flow (EGF) Mapping system (Ablamap® Software, Ablacon, Wheat Ridge, CO) is a technology based on a novel algorithm being able to 1) discriminate between active sources of excitation and passive rotations, which do not generate action potentials; and 2) estimate the average activity of such a source during a time interval such as one minute.¹¹ It has been shown that only those sources that are generating excitation and that are active more than a quarter of the time are significant predictors for AF recurrence after PVI.¹² The EGF system uses a velocity vector matrix created through an optical flow analysis applied on surface voltage movies created using a minimal energy algorithm from endocardial unipolar electrograms. The analysis is conducted with the 64-electrode mapping basket catheter, which was also used for FIRM-guided rotor mapping.

The goal of this clinical trial is to evaluate this novel mapping software for identifying AF sources in humans with persistent AF to optimize ablation success in this challenging and heterogeneous patient population. To date no EGF-guided ablation of AF sources has been performed in a controlled trial.

1.1 Test Device Description

The Ablacon, Inc. Ablamap® Software is an electrophysiological mapping software application designed to analyze the flow of excitation in cardiac tissue. The software uses an optical flow algorithm to process recorded files of electrocardiogram (ECG) signals from multiple-electrode mapping catheters (e.g. basket catheters) by transforming the time domain waveform information from all electrodes into space domain information and calculating velocity vectors of the electrographic action potential flow (EGF) for each point in space.

The output is a set of files that graphically depict flow directions (velocity vectors) and sources where the flow is generated. The software discriminates between sources that may be focal or rotational and passive rotations that are not sources; detects spatial and temporal stability of sources; and defines the activity of sources as the percentage of time a source is at its maximum stability.

The Ablamap® Software is stand-alone software installed on a standard, commercially available desktop or laptop computer. The software processes ECG data files that have been saved on a USB memory device, the computer, or a data server. The software does not control or interface with any medical device. There is no user or patient contact.

The Ablamap® Software is an innovative AF mapping device compared with current devices on the market in that it can quantify the activity of rotors or focal impulses, which are sources of atrial fibrillation and distinct from passive rotors, which are not. It also identifies focal impulses, which are sources that break across/through the atrium wall. Other system(s) cannot quantitatively analyze active and passive rotations and struggle to consider focal impulses because they do not rotate. The quantitative analysis allows monitoring of AF source behavior during therapy guidance and ultimately verification of successful ablations (Bellmann et al 2019).

1.2 Intended Treatment Population

The Ablamap® Software is intended to treat patients with atrial fibrillation for whom electrophysiology procedures have been prescribed.

2 STUDY PROTOCOL

2.1 Objective

The objective of this study is to evaluate the reliability of the Ablacon Electrographic Flow (EGF) algorithm technology (Ablamap® Software) to identify AF sources and guide ablation therapy in patients with persistent atrial fibrillation.

2.2 Primary Endpoints

The primary endpoint events for this trial to assess the safety and effectiveness of the Ablamap® Software System to guide therapy for the treatment of persistent atrial fibrillation are as follows:

- Primary Safety Endpoint: Freedom from serious adverse events (SAEs) related to the procedure through 7 days following the Randomization procedure.
- Primary Effectiveness Endpoint: Acute procedure success defined as the ability to successfully ablate AF sources identified by the EGF algorithm.

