1 PROTOCOL SUMMARY

Objective	The objective of this study is to evaluate the reliability of the Ablacon Electrographic Flow (EGF) algorithm technology (Ablamap® Software) to identify AF sources and guide ablation therapy in patients with persistent atrial fibrillation
Test Device	Ablacon Electrographic Flow Algorithm Technology (Ablamap® Software)
Study Design	The study is a prospective, randomized, controlled multi-center study.
Planned Subject Sample Size	A maximum of 100 subjects will be enrolled in this study.
No. of Sites	Subjects will be enrolled at up to five (5) investigational sites in Europe.
Primary Safety Endpoint	Freedom from serious adverse events (SAEs) related to the procedure through 7 days following the Randomization procedure.
Primary Efficacy Endpoint	Acute procedure success defined as the ability to successfully ablate AF sources identified by the Ablacon EGF algorithm
Secondary Efficacy Endpoints	
 • Consistency of sources identified by the Ablacon EGF algorithm between the randomization procedure and any applicable subsequent EGF-guided ablation procedures as assessed by remapping of the atria and the algorithm's ability to reproduce sources identified by a previous procedure • Freedom from documented episodes of atrial fibrillation recurrence following the blanking period (90 days post procedure through 12 months). • Total number of EGF source ablations • Total time of EGF source ablations • Total fluoroscopy time and dose • Overall procedure time
Inclusion Criteria	
 1. Suitable candidate for intra-cardiac mapping and ablation of atrial arrhythmias. 2. Above eighteen (18) years of age or of legal age to give informed consent specific to state and national law. 3. Subjects with a history of documented symptomatic, persistent or longstanding persistent atrial fibrillation ≤ 36 months. 4. Subject agrees to comply with study procedures and be available (geographically stable) for follow-up visits for at least 12 months.

	
5. Treatment of atrial fibrillation with ablation therapy presenting with recurrent symptoms of AF (not applicable to De Novo subjects)
																

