2.5 Enrollment/Screen Failures

A subject is considered enrolled after signing the informed consent. All enrolled subjects will then proceed to complete the screening and baseline tests. If they do not meet the eligibility criteria, they will be exited from the study and will not count towards the treated study population.

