2.6 Randomization

A 1:1 blocked randomization scheme stratified by site will be used for randomization. Subjects will be randomized based on the results of the pre-procedure EGF mapping procedure. If the subject has identifiable AF sources above a pre-specified threshold, the subject will be randomized to either: 1) immediate EGF-guided radiofrequency ablation with the Ablamap® Software System; or 2) EGF mapping followed by a cardioversion procedure, if required. If the subject is randomized to no treatment, the investigator may choose to cardiovert the subject prior to ending the procedure. Subjects that have no identifiable sources or sources below the threshold will not be randomized. The investigator may choose to ablate those subjects per their standard ablation practices.

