2.7 Statistical Analysis

Continuous variables will be reported as mean \pm standard deviation and where appropriate as median \pm interquartile range. Continuous variables were compared with unpaired t-test, and proportions were compared with the chi-square test. A two-sided p-value of $< .05$ was considered to indicate a statistically significant difference. For the secondary effectiveness endpoint of freedom from AF from the 90-day post-procedure blanking period through 12 months of follow-up, the length of time to recurrence of AF in each group was analyzed using Kaplan-Meier curves. Data were managed using Microsoft Excel and statistical analyses calculated using Microsoft Excel or Matlab.

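### The primary safety endpoint counts only SAEs attributed to the procedure, in a trial where the operator knows the arm, and no count free of attribution is planned beside it

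*Combined protocol and SAP*

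**What the plan says.** The Protocol Summary and Section 2.2 give the same primary safety endpoint: "Freedom from serious adverse events (SAEs) related to the procedure through 7 days following the Randomization procedure". Relatedness is part of the definition.

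Section 2.6 sets the arms as "1) immediate EGF-guided radiofrequency ablation with the Ablamap® Software System; or 2) EGF mapping followed by a cardioversion procedure, if required". For the second arm it adds: "If the subject is randomized to no treatment, the investigator may choose to cardiovert the subject prior to ending the procedure". Allocation is described as follows: "A 1:1 blocked randomization scheme stratified by site will be used for randomization".

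Three statements bear on the denominator. The Protocol Summary says "A maximum of 100 subjects will be enrolled in this study". Section 2.5 counts enrolment from consent: "A subject is considered enrolled after signing the informed consent". Section 2.6 removes some mapped subjects from randomization: "Subjects that have no identifiable sources or sources below the threshold will not be randomized".

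On judging relatedness, the document is nearly silent. Section 3.4 mentions the investigator's opinion on relatedness, but only as a ground for withdrawing a subject. Section 3.5 cites general guidance on good practice and SAE reporting without stating a rule for this endpoint. No section defines relatedness, names who decides it for the endpoint, or describes masking or independent adjudication. Table 1 in Section 3.2 collects adverse events at the procedure and at every later visit.

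**The concern.** All mapped subjects undergo an invasive procedure, and one randomized arm is also ablated. Whoever attributes an SAE with knowledge of the arm may link the same event to the procedure more readily after ablation than after mapping alone. An operator who favours the device may do the opposite. The procedure itself also differs by arm (mapping plus ablation, or mapping with optional cardioversion), and the document does not say whether an SAE following the optional cardioversion counts.

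What is at stake is how far a reader can trust the primary safety result. With few subjects and probably few events, one or two attribution decisions can shape it. The plan offers no second count against which to see whether they did.

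**Working it through.** The plan states no event rate, margin, performance goal or sample-size derivation for safety, so it has no figure of its own to reproduce. What can be computed is how sensitive the result is to a single attribution decision.

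**Inputs**
- Enrolment cap: 100 (Protocol Summary).
- Allocation: 1:1 (Section 2.6), so nominally at most 50 per arm. Site-stratified blocks may leave the split slightly uneven.
- Fraction *f* of the 100 who are randomized: not stated. Screen failures (Section 2.5) and subjects without sources above the threshold (Section 2.6) both reduce it. A range is shown.
- Test for proportions: chi-square, two-sided 0.05 (Section 2.7). This is a general statement, not tied to the safety endpoint.

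**Step 1: one reclassified event, arms compared.** The endpoint is per subject, so take a subject whose only potentially related SAE is moved in or out of the count. With n = 100*f*/2 per arm, that arm's rate, and hence the arm difference, moves by 100/n points.

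| Randomized fraction *f* (assumed below 100%) | n per arm | Shift, points |
|---|---|---|
| 100% | 50 | 100/50 = 2.0 |
| 80% | 40 | 100/40 = 2.5 |
| 60% | 30 | 100/30 = 3.3 |
| 50% | 25 | 100/25 = 4.0 |
| 40% | 20 | 100/20 = 5.0 |
| 30% | 15 | 100/15 = 6.7 |

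Only the first row follows from the documents, and it is the floor. The others show what happens as fewer subjects are randomized.

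**Step 2: one reclassified event, pooled rate.** If safety is reported as a single rate over 100 subjects, the shift is 100/100 = 1 point.

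**Step 3: illustration with the named test.** For *a* events against 0 with n per arm, the uncorrected chi-square is 2n*a*/(2n − *a*).
- n = 50: 3 v 0 gives 300/97 = 3.09, p = 0.079. 4 v 0 gives 400/96 = 4.17, p = 0.041.
- n = 25: 3 v 0 gives 150/47 = 3.19, p = 0.074. 4 v 0 gives 200/46 = 4.35, p = 0.037.
- Fisher's exact test stays above 0.05 throughout: 0.242 to 0.118 at n = 50, and 0.235 to 0.110 at n = 25.

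If the arms were compared with that chi-square test, one attribution decision could move the p-value across 0.05. The event counts are chosen for illustration and are not predictions.

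**The case against.** The strongest reply is that Section 2.2 gives the endpoint without a comparator, hypothesis or margin. The chi-square sentence in Section 2.7 is general, so an arm difference in safety may never be the analysis. This stands, and the size is therefore given for both a comparison and a pooled rate. It also means that Step 3 does not show a planned conclusion being overturned.

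Second, 100/n describes any binary endpoint in a trial of this size. It measures small numbers, not attribution bias. That is also true. The figure shows how much one decision matters, not how often decisions would go wrong.

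Third, a reader might infer a definite bias. Suppose true SAE rates are equal at 6% to 10%, and attribution is 90% in one arm and 60% in the other. The reported rates would then be 5.4% v 3.6% (0.06 × 0.9 and 0.06 × 0.6) up to 9% v 6%, a false difference of 1.8 to 3.0 points. Nothing in the documents supplies these rates or a direction, and the standard error of such a difference at 25 to 50 per arm is about 4 to 7 points. The calculation illustrates the mechanism and estimates nothing. A reader might also suppose that few SAEs within a week of an invasive procedure are truly unrelated, so that the filter is pointless. The documents give no basis for that, and the point does not need it.

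Fourth, adverse events are collected anyway, and the SAE-reporting guidance cited in Section 3.5 may lead to a full listing. That may be so, but an analysis decided after the data are seen does not protect the primary result as a prespecified one would.

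**Conclusion.** The concern holds in a limited form. The primary safety endpoint depends on a relatedness judgement that may be made with knowledge of the arm. No masked adjudication is described, and no attribution-free count is planned. Differential attribution could bias the result either way. That the operator knows the arm follows from the nature of the two arms; that this operator makes the endpoint judgement is likely but not stated.

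The size is conditional. If the arms are compared, one reclassified subject moves an arm's rate by at least 2 points, which assumes all 100 are randomized at 50 per arm. It is 4 points if half are randomized, which is an assumption, and more below that. For a pooled rate over 100 subjects it is 1 point.

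A reader might infer that a fixed range of 2 to 4 points is established, or that the safety result will be biased. The documents support neither: only the 2-point floor follows from them, and the direction and extent of any bias are unknown. The weakness does not invalidate the trial. It touches a primary endpoint and is cheap to reduce.

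**What to change.** In Section 2.2, keep the primary safety endpoint and add a prespecified sensitivity analysis:

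- Count subjects with any SAE with onset through day 7, whatever its attribution, with exact 95% confidence intervals.
- Report this by randomized arm, and separately for subjects who were mapped but not randomized. The latter undergo the mapping, and under Section 2.6 may be ablated, so a table of randomized arms alone would omit them.
- List each SAE judged unrelated, with the reason.
- State that the safety conclusion will be qualified if the two counts differ materially. A rule that safety must be shown on both counts could not be applied, because the plan has no criterion for a safety conclusion.

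Classify by onset date. The phone contact at 7 ± 3 days can fall on day 4, so SAEs starting on days 5 to 7 may first be recorded at the 3-month visit, where Table 1 also collects adverse events.

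This makes the influence of attribution visible but does not remove it. Naming who judges relatedness, and stating what counts as the procedure in each arm, would help further. Masked adjudication could be added, but the sensitivity analysis does not depend on it.

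The cost is some wording and one extra table with a listing, from adverse events already collected. The all-SAE rate may look slightly less favourable than the related-only rate.

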2.3 Secondary Endpoints

- Consistency of sources identified by the Ablacon EGF algorithm between the Randomization procedure and any applicable subsequent EGF-guided ablation procedures
- Freedom from documented episodes of AF recurrence following the blanking period (90 days post-ablation) through 12 months.
- Total number of EGF source ablations
- Total time of EGF source ablations
- Total fluoroscopy time and dose
- Overall procedure time

2.4 Study Design

The FLOW-AF study is a prospective, multi-center study conducted to assess the safety and efficacy of the Ablamap® Software System for patients with a history of persistent atrial fibrillation. This study will enroll up to 100 subjects. Patients that present with persistent atrial fibrillation, meet eligibility, and have had a previous ablation procedure prior to being enrolled in the study will be eligible for enrollment. All subjects must be in AF at the time of the procedure.

2.5 Enrollment/Screen Failures

A subject is considered enrolled after signing the informed consent. All enrolled subjects will then proceed to complete the screening and baseline tests. If they do not meet the eligibility criteria, they will be exited from the study and will not count towards the treated study population.

2.6 Randomization

A 1:1 blocked randomization scheme stratified by site will be used for randomization. Subjects will be randomized based on the results of the pre-procedure EGF mapping procedure. If the subject has identifiable AF sources above a pre-specified threshold, the subject will be randomized to either: 1) immediate EGF-guided radiofrequency ablation with the Ablamap® Software System; or 2) EGF mapping followed by a cardioversion procedure, if required. If the subject is randomized to no treatment, the investigator may choose to cardiovert the subject prior to ending the procedure. Subjects that have no identifiable sources or sources below the threshold will not be randomized. The investigator may choose to ablate those subjects per their standard ablation practices.

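### Randomization is stratified by site but the between-arm comparisons in section 2.7 ignore site, which wastes precision if outcomes differ by site

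*Combined protocol and SAP*

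**What the plan says.** Section 2.6 sets the allocation: "A 1:1 blocked randomization scheme stratified by site will be used for randomization". The Protocol Summary gives the number of strata: "Subjects will be enrolled at up to five (5) investigational sites in Europe". Block size is not stated.

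Section 2.7 gives the tests: "Continuous variables were compared with unpaired t-test, and proportions were compared with the chi-square test". The significance level is two-sided 0.05. For freedom from AF after blanking, "the length of time to recurrence of AF in each group was analyzed using Kaplan-Meier curves"; no test and no effect estimate is named for that endpoint. Site does not appear in any analysis, as a stratum or as a covariate.

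The outcomes on which arms can be compared are freedom from AF recurrence, procedure-related serious adverse events (SAEs), procedure time and "Total fluoroscopy time and dose". The primary effectiveness endpoint is different: "Acute procedure success defined as the ability to successfully ablate AF sources identified by the EGF algorithm". It exists only where sources are ablated, so it offers no between-arm comparison to stratify.

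**The concern.** Stratified blocks keep the arms nearly balanced within each site, so differences between sites largely cancel from the arm difference. An analysis that pools all subjects still puts those differences into its standard error. It therefore reports more uncertainty than the design left, and true differences are harder to detect.

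Some site variation is plausible from the plan itself. Cardioversion of untreated randomized subjects is at the investigator's choice (section 2.6). AF detection depends partly on unscheduled visits and on Holter recordings for which Table 1 gives no duration. Fluoroscopy and procedure times depend on operator and laboratory.

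Precision is also scarce. Enrollment is capped at 100 and counted early: "A subject is considered enrolled after signing the informed consent". Screen failures and subjects without sources above the threshold are not randomized, so the randomized number will probably be below 100.

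**Working it through.** The plan states no power, effect size or standard deviation, so there is no figure of its own to reproduce.

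**1. Formula for a continuous outcome.** Let r be the share of outcome variance due to site, σ² the total variance and N the number randomized 1:1.

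- True variance of the arm difference under within-site balance: 4(1 − r)σ²/N.
- Variance the unpaired t-test estimates: 4σ²/N.
- Standard error (SE) too wide by 1/√(1 − r). Actual two-sided alpha = 2[1 − Φ(1.96/√(1 − r))].

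| r | SE ratio | Actual alpha |
|---|---|---|
| 0.05 | 1.026 | 0.044 |
| 0.10 | 1.054 | 0.039 |
| 0.20 | 1.118 | 0.028 |
| 0.30 | 1.195 | 0.019 |

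For N = 100 and σ = 1, the t-test SE is 0.200. The true value is 0.200 × √0.90 = 0.190 at r = 0.10 and 0.200 × √0.70 = 0.167 at r = 0.30. Simulated trials gave 0.189 and 0.170.

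**2. Power by simulation.** From the plan: 1:1 allocation, site-stratified blocks, five sites, two-sided 0.05, and 100 subjects (all taken as randomized). Assumed:

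- Equal sites of 20, blocks of 4, 6,000 trials per cell.
- Survival: exponential over 275 days (365 − 90), control freedom 35%, hazard ratio 0.5, site log-hazard SD 0, 0.25, 0.5 or 1.
- Binary: 35% vs 62%, site logit SD 0, 0.25, 0.5 or 1.
- Continuous: difference of 0.5 within-site SD, intraclass correlation (ICC) 0, 0.05, 0.10 or 0.30.

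Power in %, ignoring site / using site:

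| Site spread | t-test / linear model | Chi-square / CMH | Log-rank / stratified log-rank |
|---|---|---|---|
| None | 70.3 / 70.0 | 80.0 / 79.7 | 70.4 / 69.2 |
| Mild | 68.1 / 69.4 | 77.8 / 77.6 | 70.1 / 70.5 |
| Moderate | 66.8 / 69.8 | 74.5 / 74.8 | 66.2 / 70.3 |
| Very large | 58.1 / 69.0 | 64.5 / 68.8 | 51.4 / 68.2 |

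The simulation error of one power figure near 70% is √(0.7 × 0.3/6000) = 0.6 points. Repeating the survival runs gave 71.4/70.5, 70.0/70.0, 65.6/69.5 and 49.6/67.8%.

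The mean SE ratio (t-test to linear model) was 1.00, 1.02, 1.045 and 1.16. The last is below the 1.195 above. This is what one expects when five site effects are drawn at random, since their observed variance averages 4/5 of nominal: √(1 + 0.8 × 0.30/0.70) = 1.16.

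**3. False positives** (% rejecting under no effect, same four spreads):

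| Test | Ignoring site | Using site |
|---|---|---|
| Log-rank | 4.9, 4.7, 3.6, 2.0 | 5.1, 5.1, 5.0, 5.1 |
| Chi-square / CMH | 4.5, 4.9, 4.1, 4.1 | 4.5, 4.9, 4.5, 5.4 |
| t-test / linear model | 5.2, 4.6, 4.2, 2.4 | 5.2, 5.1, 4.9, 4.5 |

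At ICC 0.30 the nominal 95% t-test interval covers 97.0%.

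**4. What the spreads mean for AF freedom.** Control freedom at sites one SD either side of 35% is 0.35^exp(±SD):

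- SD 0.25: 26% and 44%.
- SD 0.5: 18% and 53%.
- SD 1: 6% and 68%.

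**5. Small, unequal sites.** Power in %, ignoring site / using site / using site with sites under 8 pooled:

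| Case | Log-rank | Chi-square / CMH | t-test / linear model |
|---|---|---|---|
| 60 as 40/10/5/3/2, no spread | 49.0 / 47.7 / 48.1 | 56.7 / 54.7 / 55.9 | 47.6 / 46.5 / 47.2 |
| Same, very large spread | 35.8 / 45.0 / 44.3 | 44.1 / 46.1 / 46.3 | 40.0 / 47.1 / 45.8 |
| 40 as 24/6/4/3/3, no spread | 35.2 / 33.0 / 34.8 | not run | not run |

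**The case against.** The strongest reply is that the loss is conditional and never anti-conservative. It has several parts, and most of them stand as limits on size.

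- **The biggest losses belong to a test the plan does not contain.** The 4.1 points (70.3 − 66.2) and 16.8 points (68.2 − 51.4) are both log-rank. For the named tests the moderate-spread loss is 3.0 points (t-test) and 0.3 points (chi-square). This stands. But AF freedom needs some test, and when one is added it should match the randomization.
- **The moderate label is generous for AF freedom.** It means 18% against 53% between sites, a threefold difference. This stands; milder spreads cost almost nothing.
- **The other endpoints gain little.** Fluoroscopy and procedure times will probably differ between an ablated and a non-ablated arm whatever test is used. For rare SAEs (assumed 2% vs 10% or 15%), CMH gained about 1 to 3 points at N = 100, of which 1.4 to 1.7 appear with no site effect. At N = 60 it changed power by −1.1 to +0.5. So the case for CMH on safety is consistency with the design, without material harm, rather than power.
- **Section 2.7 does not say which variables or groups its t-test and chi-square compare,** and section 2.2 states no between-arm safety hypothesis. This stands. The point applies only where arms are compared.
- **Stratifying can cost power in tiny sites.** True, by about 1 to 2 points in the cases shown, and pooling recovers part of it.

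None of this gives a reason to randomize by site and then leave site out of the analysis.

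**Conclusion.** The concern holds. The plan stratifies by site and analyses as if it had not. The consequence is lost precision if sites differ, with no bias and no excess of false positives.

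With 100 randomized at five equal sites, the loss is about zero for no or mild spread, 0 to 4 points of power for moderate spread and 4 to 17 points for very large spread. Standard errors for continuous outcomes are too wide by 0, 2, 4 to 5 and 16% across the four spreads. These sizes rest on assumed site spreads, effect sizes and block size, none of which the documents give, and on 100 randomized, which is the ceiling. AF freedom is where the point matters most. The primary effectiveness endpoint is unaffected. It is worth correcting because the correction is cheap, but it is not a threat to validity.

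**What to change.** In section 2.7, for between-arm comparisons only:

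1. Freedom from AF: keep the Kaplan-Meier curves, and add a site-stratified log-rank test and a site-stratified Cox hazard ratio with 95% confidence interval. This also supplies the missing test and effect estimate.
2. Proportions, including procedure-related SAEs: Cochran-Mantel-Haenszel over site.
3. Fluoroscopy and procedure times: a linear model with treatment and site.
4. Small sites: prespecify pooling, for example all sites with fewer than 8 randomized subjects form one stratum. The cut-off is a convention and should be fixed in advance.
5. Leave the primary effectiveness endpoint unstratified.

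The cost is wording. Site is known from the randomization, and section 2.7 already names Matlab; the sponsor should confirm that the stratified methods are available in the software it uses. If sites do not differ, the price is about 0 to 2 points of power. With the pooling rule, the cases shown lose 0.4 (47.6 − 47.2) to 0.9 (49.0 − 48.1) points.

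Much of section 2.7 is in the past tense. If between-arm results have already been seen, the site-stratified analyses can no longer count as prespecified and should be labelled as sensitivity analyses.
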